Aim 1 - To optimize YST+YM for feasibility and acceptability. Outcome: Semi-structured interviews and rating scales will identify the most and least preferred elements of the YM module. Response rates to automated text-messages will also be used to evaluate message appeal.

Aim 2 - To test target engagement: does YST+YM increase utilization of interpersonal emotionregulation strategies and social support among adolescents with recent suicidal ideation or attempts? Hypothesis: over 12 weeks of YST+YM, subjects will demonstrate increases in: (a) the number of weekly contacts initiated to supportive adults in their lives, (c) the utilization of interpersonal emotion regulation strategies, and (c) their perceived sense of social support. These gains will be maintained at 3-month post-intervention follow-up.

Aim 3: Estimate prevalence of clinical outcomes for planning of subsequent trials - what is the average rate of clinical over the course of intervention and through 3-month follow-up? Outcome: Estimates of changes in distal targets, including anxiety, depression, and suicidal ideation and attempts for the planning of larger subsequent trials.

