This study, encompassing both phases one and two, utilizes a one-armed, within-subjects design and will run for roughly 24 total months. Youth subjects will receive the intervention (YST+YM) and will each be assessed at 4 timepoints: prior to initiating intervention (baseline, week 1), the intervention midpoint (week 6-7), the conclusion of the intervention (post-test, week 12), and then 3 months after the intervention concludes (follow-up, 24 weeks). Adult support team members will be assessed only at post-test (week 12).

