5. SUBJECT POPULATION

Number of Subjects: This study includes three sets of subjects, including (1) youth patients, (2) parents, and (3) their respective adult support team members. The subject population is the same for both phases one and two.

• Youth patients: We will enroll approximately n = 60-70 total adolescent patients in the Child and Adolescent Partial Hospitalization Service (CAPHS). The first n = 5-10 of these will be used to refine and optimize the feasibility and acceptability of YST+YM. All

Page 4 of 64 Version Date: 12/13/21 subjects will be used to evaluate target engagement. Based on consultation with CAPHS clinical director, [name] (LMSW-R), greater than 80% of patients are expected to be eligible for participation. Of eligible patients, roughly 50% are estimated to enroll in the study. Again based on consultation with [name], 75% of the initially enrolled patients are expected to complete the study. Thus, we will screen approximately 165 patients to identify 130 eligible subjects, of which 65 are expected to enroll. Given low attrition for comparable clinical programs in CAPHS (i.e., a year of pilot implementation of traditional YST in that clinic), we conservatively estimate a 25% attrition rate. Attrition will be handled with an intent-to-treat design. Given these considerations, we anticipate n = 50 subjects will provide follow-up data, providing a sufficient sample size to detect a signal for intervention target engagement.

- Parents / legal guardians: We will invite one parent / legal guardian per enrolled youth to provide feedback on the intervention, proxy-ratings of the youth's emotional well-being, as well as self-report of their own well-being. Based on consultation with clinic staff who regularly interact with this population, recruitment and retention rates for parents are expected to be roughly 80% per youth who completes the study. Thus, for the roughly n = 50 youth subjects who provide full follow-up data, we expect roughly n = 40 parents / guardians to complete all measures. This is a sample size sufficient to refine the intervention with informal feedback and to further evaluate target engagement as assessed by proxy-report.

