17. DATA ANALYSIS PLAN

For Aim 1, we will use descriptive statistics to gauge achievement of feasibility and acceptability thresholds for patients. Means above 3.5 (on a 5 point scale) will be regarded as adequate feasibility and acceptability.

For Aim 2, a linear mixed effects model will be used to evaluate (a) overall frequency of responding to text messages and (b) trends in text response rates over time. Aim 2 will also utilize generalized linear mixed effects models (fixed effect for time, with a random effect for individual) to evaluate changes in intervention target scores over time. Each of the intervention targets will serve as the outcome variable in its own separate model.

For Aim 3, means and proportions will be estimated and retained for future study planning.

A power analysis evaluating these models was conducted via simulation. For the linear mixed effects models (Aims 2), assuming a moderate effect size (d = .50) and moderate within-subject shared variance attributable (ICC = .05), simulations show this model will have adequate power (.82) to detect target engagement over the course of the intervention. Because Aims 1 and 3 utilize only descriptive statistics and require no statistical inference, no power analysis was conducted.

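### Does the Aim 2 model need a stated time coding and a named contrast before it can test a week-12 gain that is held at week 24?

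*Combined protocol and SAP*

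**What the plan says.** Section 2, Aim 2, has two parts. The first is that "over 12 weeks of YST+YM, subjects will demonstrate increases in" three targets: contacts initiated to supportive adults, interpersonal emotion regulation, and perceived support. The second is that "These gains will be maintained at 3-month post-intervention follow-up".

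Section 4 (Study Design) gives each youth four assessments: baseline, weeks 6-7, week 12 and week 24.

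Section 17 gives one form of model for every target: "generalized linear mixed effects models (fixed effect for time, with a random effect for individual) to evaluate changes in intervention target scores over time". Each target has its own model. The power statement assumes d = .50 and ICC = .05 and reports "adequate power (.82) to detect target engagement over the course of the intervention". Section 17 does not give the coding of time, the visits that enter the model, a contrast, or a criterion for maintenance.

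Section 5 expects 65 youths to enrol, handles attrition by intent to treat, and states that "we anticipate n = 50 subjects will provide follow-up data".

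**The concern.** Aim 2 is the only aim with inferential testing and a power claim, and maintenance is half of its hypothesis. The phrase about a fixed effect for time can be read in three ways, and they do not answer the same question:

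- **Time as a four-level factor.** The visit means are all estimated, but if only the overall 3-df test were reported, it could not say where the change occurred.
- **Time as one linear term over weeks 0, 6, 12 and 24.** The slope cannot tell a gain held from week 12 from one that first appears at week 24, and it largely misses a gain that fades.
- **Weeks 0 to 12 only.** The power sentence could suggest this. The rise is tested and the week-24 data are not used.

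At stake is whether the coding could be picked after the data are seen, and whether a significant time effect could be reported as maintained target engagement when it shows no such thing.

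**Working it through.** **Inputs.** From section 17: d = .50, ICC = .05, power .82. From section 5: 65 enrolled, about 50 with follow-up. From section 4: visits taken as weeks 0, 6, 12 and 24. Assumed, because the documents do not state them: two-sided alpha .05, the number of youths in the plan's simulation, a continuous outcome with total SD 1, and the mean patterns below. ICC .50 is an assumed upper value.

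**1. The plan's own figure.** In a random-intercept model the week-12 minus baseline contrast has SE = sqrt(2(1 - ICC)/n).

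- n = 65: sqrt(1.90/65) = .171; .50/.171 = 2.92; power .83 (normal), .821 (paired t), .829 (model df).
- n = 50: sqrt(1.90/50) = .195; .50/.195 = 2.56; power .73, .710 and .722 in the same order.

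So .82 fits the gain during the intervention at the expected enrolment. With 50 complete cases a one-sided paired t would give .81.

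**2. The readings under different true patterns.** Means at weeks 0, 6, 12, 24: held (0, .25, .50, .50); half faded (0, .25, .50, .25); fully faded (0, .25, .50, 0).

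- Overall test: noncentrality = n × Σ(m - mean)²/(1 - ICC), with 3 and 3(n - 1) df. The sum of squares is .1719 for the held and the fully faded pattern alike, and .125 for half faded.
- Linear slope: b = Σ(t - 10.5)m/315, SE = sqrt((1 - ICC)/(315n)). Held: 6.375/315 = .0202 per week. Half faded: 3.0/315 = .0095. Fully faded: -.375/315 = -.0012.

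Power at n = 50, ICC .05 (ICC .50 in brackets):

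| True pattern | Overall 3-df test | Four-visit slope | Week 12 minus baseline, model df |
|---|---|---|---|
| Held | .701 (.945) | .735 (.946) | .722 (.940) |
| Half faded | .548 (.846) | .230 (.390) | .722 (.940) |
| Fully faded | .701 (.945) | .053 (.055) | .722 (.940) |

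The top row is the pattern that Aim 2 predicts. There the slope is slightly ahead of the direct contrast; at n = 65 the figures are .840 and .829. The slope's collapse belongs to the lower rows.

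**3. What factor coding gives.** With baseline as reference, the week-12 coefficient is the gain over the intervention and the week-24 coefficient is the gain still present at follow-up. Their difference is the change from week 12 to week 24. Nothing has to be added to the model to obtain these.

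**4. What any coding could say about maintenance.** The 95% half-width for week 24 minus week 12 at n = 50 is about .38 to .39 SD at ICC .05 (1.96 × .195 = .38; .39 with paired t) and about .28 SD at ICC .50. Power to detect loss of half the gain (.25 SD) is about .24 to .25 at ICC .05 and .41 to .42 at ICC .50. The limit on a maintenance claim is the sample size, whichever contrast is written down.

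**The case for a change.** The strongest case for acting is that one sentence permits analyses that disagree on the same data. A .50 SD gain at week 12 that has gone by week 24 has power .05 under a straight line and .70 under the overall factor test, and that second figure is the same if the gain had held. The figure of .82 cannot settle which analysis was meant, because at n = 65 the overall test (.824) and the week-12 contrast (.821 to .829) both match it. Leaving coding and contrast open invites a choice made after the data are seen.

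The omission stands: neither a coding nor a contrast for maintenance appears anywhere in the documents. The inference to harm is weaker:

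- Nothing says that the overall test would be the reported result. A factor in a mixed model produces a coefficient for each visit.
- Nothing says that time is linear. The poor slope figures need both that coding and a fading gain.
- The analyst's freedom is bounded. Section 2 fixes the direction, the 12-week interval and the later check, and section 4 schedules "the conclusion of the intervention (post-test, week 12), and then 3 months after the intervention concludes (follow-up, 24 weeks").
- The power sentence describes what was powered. It does not restrict which visits enter the model, and section 5 ties the youths with follow-up data to detecting engagement.

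A further suggestion, to replace the random intercept by an unstructured covariance, rests on a correlation pattern that the documents do not give. It also does not carry over simply to a generalized model for a count such as weekly contacts.

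**Conclusion.** No change follows. Section 17 is thin here, but the model it names can estimate both parts of the hypothesis. Sections 2 and 4 say which interval and which visit matter, and an analyst who reads Aim 2 beside section 17 would fit visits as levels and report week 12 and week 24 against baseline. The stated .82 is not shown to be wrong. Under the predicted pattern the choice of coding moves power by about .01 (.735 against .722 at n = 50; .840 against .829 at n = 65). The large losses, down to about .05, depend on a coding that the plan does not state and a course that it does not expect.

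One caution for the reader of the results: a non-significant change from week 12 to week 24 would not demonstrate maintenance, since about 50 youths leave an interval of roughly ±.28 to ±.39 SD.

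These figures assume two-sided .05, a continuous outcome, ICC between .05 and .50, and complete data at the stated n. They do not apply directly to the count of contacts. A mixed model under intent to treat would also use partial records, so week-12 power at ICC .05 should lie between the 50-youth and 65-youth values.

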4. STUDY DESIGN

This study is a two-phased, one-armed pilot trial to evaluate feasibility, acceptability, and target engagement of YST+YM. It will also facilitate estimation of clinical outcome prevalence, including suicidal ideation and attempts over the intervention period and through post-intervention follow-up.

In phase one (content refinement; n = 5-10), feasibility and acceptability will be optimized via measures of subject engagement with the intervention (i.e., text-message response rates) and with subject feedback during semi-structured interviews. We will also assess feasibility of the assessments used to measure emotion regulation, perceived social support and connectedness, and clinical outcomes (i.e., anxiety, depression, and suicidal ideation and attempts).

In phase two (pilot; n = 60-70), target engagement and prevalence of clinical outcomes will be addressed, as well as continued assessment of feasibility and acceptability of YST+YM. Consistent with specific aims above, intervention targets include engagement with treatment (i.e., initiating contact with support team members), changes in emotion regulation skills, and perceived social support and connectedness. Distal targets, including anxiety, depression, and suicidal ideation and attempts will also be assessed to establish point estimates for power analysis and sample size planning in future trials. Subject engagement with the intervention and feedback during semi-structured interviews will be used to assess feasibility and acceptability of YST+YM (following initial modification in response to phase one subject feedback).

Because the intervention lasts approximately three months per subject, the phases will be staggered, such that some subjects will be enrolled in phase two before all phase one subjects have completed their entire intervention course. For example, we anticipate that n = 5-10 phase one subjects may complete the first remote session of YST+YM within 6 weeks of the study start date. Because we collect feedback immediately following each session, this means we will have received all the information required to finalize that session's outline and content for the launch of phase two – even though these phase one subjects will have several weeks left of YST+YM overall.

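### Aim 3 leaves symptom change to simple means, which are biased if dropout is related to symptoms; the planning figures should come from a mixed model on all enrolled youth

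*Combined protocol and SAP*

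**What the plan says.** The Specific Aims (Section 2) define the Aim 3 outcome as change: "Estimates of changes in distal targets, including anxiety, depression, and suicidal ideation and attempts for the planning of larger subsequent trials". Section 4 gives the purpose of measuring these outcomes: "to establish point estimates for power analysis and sample size planning in future trials".

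The Data Analysis Plan (Section 17) gives Aim 3 one sentence: "For Aim 3, means and proportions will be estimated and retained for future study planning". It adds: "Because Aims 1 and 3 utilize only descriptive statistics and require no statistical inference, no power analysis was conducted". The mixed models in that section are assigned to Aim 2, for text-message responses and intervention targets. No analysis set, missing-data method or way of forming a change is given for Aim 3.

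On attrition, Section 5 says "we conservatively estimate a 25% attrition rate" and "Attrition will be handled with an intent-to-treat design". The second phrase is not defined further.

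Section 15 (Subject Withdrawals) takes youth out of both study and treatment when they are hospitalized for psychiatric reasons, and gives a suicide attempt as one example. It keeps data already collected unless the subject asks otherwise, and it seeks replacements for withdrawn youth while time allows.

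**The concern.** A change estimated from simple means is sound only if those who are lost resemble those who stay. Here the plan itself gives a reason to doubt that: psychiatric hospitalization ends follow-up, and it is closely tied to depression, ideation and attempts. Replacement adds new baselines without recovering the lost outcomes.

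This is bias in the estimate, separate from its precision. The numbers are meant to be carried into the sample size of a later trial, where a false change of either sign would persist. The Aim 2 method already uses every youth's observed visits and could be applied to the Aim 3 scores without new data.

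**Working it through.** **1. The plan's own sample flow.** Section 5 says "Thus, we will screen approximately 165 patients to identify 130 eligible subjects, of which 65 are expected to enroll". 165 × 0.80 = 132 (130 stated); 130 × 0.50 = 65; 65 × (1 − 0.25) = 48.75, against about 50 stated. The figure reproduces. For 60 to 70 enrolled the range is 45 to 52.5. Replacements would alter these counts.

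**2. Closed-form bias, loss depending on baseline score.** Assumptions that are not in the documents: standardized scores with higher meaning worse, no true change, logistic dropout on baseline with the intercept set to give 25% loss, odds ratio 1.5 to 3 per SD, and correlation r between baseline and week 24 of 0.5 or 0.7. The ICC of .05 is the plan's Aim 2 figure. Let m be the mean baseline score of those who stay.

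- Change in visit means = r·m − 0 = r·m
- Completers' paired change = r·m − m = (r − 1)·m

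| Odds ratio per SD | m | Visit means, r = .05 / .5 / .7 | Completers, r = .05 / .5 / .7 |
|---|---|---|---|
| 1.5 | −0.0984 | −0.005 / −0.05 / −0.07 | +0.09 / +0.05 / +0.03 |
| 2 | −0.1595 | −0.008 / −0.08 / −0.11 | +0.15 / +0.08 / +0.05 |
| 3 | −0.2279 | −0.011 / −0.11 / −0.16 | +0.22 / +0.11 / +0.07 |

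Negative is false improvement and positive is false worsening. The two simple estimators err in opposite directions. At r = .05 visit means are nearly unbiased, but completers' paired change is then at its worst.

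**3. Simulation over four visits.** N = 65, no true change, about 25% lost by the last visit, 1,500 runs per setting. Dropout log-odds are 0.5 or 1.0 per SD at each visit. The model has a random intercept and categorical visit, fitted by generalized least squares with known ICC. Bias is in SD units.

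| Loss depends on | ICC | Visit means | Completers | Mixed model |
|---|---|---|---|---|
| nothing | .5 | −0.004 | −0.002 | −0.003 |
| last observed score | .05 | −0.004 to −0.015 | +0.042 to +0.075 | +0.002 to −0.003 |
| last observed score | .5 | −0.063 to −0.119 | +0.023 to +0.035 | +0.002 to −0.004 |
| unseen current score | .05 | −0.048 to −0.084 | −0.039 to −0.071 | −0.047 to −0.083 |
| unseen current score | .5 | −0.090 to −0.161 | −0.023 to −0.042 | −0.048 to −0.087 |

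Completers' bias is smaller here than in step 2 because dropout follows the latest score rather than baseline alone. The model removes the bias when loss depends on observed scores. When loss depends on the unseen score, it roughly halves the visit-mean bias at ICC .5 and removes almost none at .05. In that case completers' paired change is closer to zero than the model.

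**4. Attempts.** Section 2 cites 30% reattempting within a year among hospitalized attempters. Applying that rate here, at a constant hazard, is an assumption: 1 − 0.70^(24/52) = 0.152, or about 10 of 65. Let a share h of attempters be withdrawn before the attempt is recorded, with the rest of the 25% loss at random. The observed proportion is then p(1 − h)/(1 − ph). With p = 0.15:

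- h = 25%: 0.1125/0.9625 = 11.7%
- h = 50%: 0.075/0.925 = 8.1%
- h = 100%: 0%

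**The case against.** - **The plan does not commit to means over whoever attends each visit.** That is the natural reading of Section 17, but a reader who takes it as stated is inferring it. This stands. It does not rescue the plan, because the other simple reading, completers' paired change, is also biased when loss depends on observed scores.
- **There is no contradiction with intent-to-treat.** A reader might infer one between Sections 5 and 17. In a one-arm study the term says who is analysed, not how missing values are handled, and Section 15's retention of available data fits available-case means. The term is undefined; the sections do not conflict.
- **The direction is not fixed.** A reader might infer that dropout must appear as improvement. That needs worse-off youth to leave more often and depends on the estimator.
- **The sizes rest on assumed inputs.** The odds ratios and the correlations of 0.5 and 0.7 are not in the documents. The ICC of .05 is, but it was set for the Aim 2 targets and may be low for symptom scores.
- **The bias is modest beside sampling error.** The standard error of the visit-mean change is √(1/49 + 1/65 − 2r/65), or 0.14 SD at r = 0.5 and 0.12 at 0.7. The bias is below one standard error at 0.5 and about 0.6 to 1.3 at 0.7. This stands and limits the urgency, but a planning estimate should not add avoidable bias to its imprecision.
- **The mixed model is not a full repair.** This also stands. Withdrawal at hospitalization can depend on scores that are never seen.

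**Conclusion.** The concern holds in limited form. Simple means and proportions are a weak choice for Aim 3, given that the plan promises changes, will use them for planning, expects 25% attrition and withdraws youth on psychiatric hospitalization. If dropout odds rise 1.5 to 3 fold per SD of baseline score, visit means mislead by about 0.05-0.11 SD at correlation 0.5 and 0.07-0.16 SD at 0.7, towards improvement. Completers' paired change misleads by about 0.05-0.11 SD at 0.5, towards worsening. The visit-mean bias is about 0.01 SD at ICC .05 when loss follows baseline score, and zero if loss is unrelated to symptoms. The documents do not establish that the bias will occur. They leave Aim 3 exposed to it when a better method is already in the plan. The change should be made, though the study does not depend on it.

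**What to change.** In Section 17:

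- Name the Aim 3 analysis set as all enrolled youth, including those later withdrawn and replaced, and define the intent-to-treat wording of Section 5.
- For each symptom score, fit the Aim 2 type of mixed model to all observed visits with visit as a category. Keep its means, changes, SD and within-youth correlation as the planning figures. Show raw means and numbers observed beside them.
- Report missingness by visit and reason, with psychiatric hospitalization separate.
- In the attempt proportion, count attempts known to have led to withdrawal as events, with all enrolled youth as denominator. State how many have unknown status, because treating them as event-free makes the figure a lower bound.
- Show a sensitivity range for loss that depends on unseen scores, since the model does not remove that bias.
- Reconcile Sections 5, 15 and 17 on how withdrawn and replacement youth enter the estimates. No change to the withdrawal rule is proposed.

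The cost is SAP wording, one more model per score and somewhat less simple descriptive output. No new data collection is needed.
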